Subjects. After obtaining their written informed consent, 20 patients with DKD (defined as estimated GFR (eGFR) 30-59 ml/min/1.73m²) with albuminuria of 200-5000 mg/g will serve as subjects. This range of albuminuria was chosen as macroalbuminuria is associated with more adverse outcomes in patients with CKD and a previous small study found a greater reduction in albuminuria with a 5-LO inhibitor in participants with greater albuminuria at baseline.³⁰ **Relevant biological variables:** Men and women age 30-70 years of all races/ethnicities will be included. Major inclusion/exclusion criteria are presented in the table below (Table 1). Participants with GFR <30 ml/min/1.73m² are excluded as this is advanced kidney disease when complications become more common and vascular damage may not be reversible. Participants will undergo screening for eGFR at the Kidney Disease Research Center (KDRC) at the University of Colorado Anschutz Medical Campus. Estimated GFR will be calculated using the new 2021 Chronic Kidney Disease Epidemiology Collaboration (CKD-EPI) prediction equation.⁴³ Participants will be recruited from nephrology clinics at the University of Colorado and Denver Health Medical Center. Additionally, patients will be recruited from our CKD database, which contains over 300 CKD patients willing to participate in clinical trials. Feasibility of recruitment is demonstrated by prior recruitment experience of the investigative team in several CKD interventional trials⁴² (NCT02915601, NCT04600323). For this study

Table 1

Inclusion Criteria	Exclusion Criteria

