
 • Age 30-70 years • Urine albumin to creatinine ratio 200-5000 mg/g on first morning void • CKD stage 3 at time of screening (eGFR 30-59 ml/min/1.73m²) • Blood pressure <140/90 mm Hg prior to baseline visit • Use of angiotensin converting enzyme inhibitor or angiotensin receptor blocker or mineralocorticoid receptor antagonist with stable dose for 4 weeks • History of diabetes type 1 or type 2 • BMI < 40 kg/m² (FMD measurements can be inaccurate in severely obese patients). • Stable anti-hypertensive regimen for at least one month prior to enrollment • Stable diabetes regimen for at least one month prior to enrollment • Sedentary or recreationally active (<2 days of vigorous aerobic exercise as vigorous exercise may affect vascular function measurements) • Able to provide consent 	
 • Significant comorbid conditions that lead the investigator to conclude that life expectancy is less than 1 year • Uncontrolled hypertension • Factors judged to limit adherence to interventions (e.g. history of medication noncompliance, noncompliance with follow up visits, significant cognitive impairment, etc.) • Anticipated initiation of dialysis or kidney transplantation within 3 months • Current participation in another research study • Pregnancy or planning to become pregnant or currently breastfeeding • Allergy to aspirin • Severe hepatic impairment (Child-Pugh Class C) • History of major psychiatric disorder • Use of inhaled or systemic corticosteroids or long-acting beta agonists (higher risk of neuropsychiatric reaction) • Current use of phenobarbital, rifampin or carbamazepine.

Rigorous Experimental Design. A 3-month **open-label, prospective pilot study** with oral montelukast will be conducted. The study will include 3 phases: screening, baseline, and follow-up.

- **Screening:** Subjects will undergo screening for inclusion/exclusion criteria during a 1-2 week period. Participants will have urine albumin/creatinine performed and basic metabolic panel to determine eligibility.
- **Baseline:** During the baseline phase the following will be measured: 1) 24-hour albuminuria; 2) vascular function (EndoPat, aPWV); 2) serum chemistry panel; 3) urine MCP-1, sCD163 and LTE₄; and 4) plasma TNFR-1.

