- **Follow-up:** The follow-up schedule includes assessments at 3 months with monthly safety visits (either via phone, in person, or survey link). An additional safety check will be performed via phone, in person, or survey link 2 weeks after the last study visit.

Study Drug Dosing: Study drug will be received from the University of Colorado Hospital Pharmacy. Each bottle will contain 90 tablets of montelukast 10mg. Participants will receive 1 tablet daily (10mg) for the entire 3 months. The tablet will be taken in the evening per manufacturer recommendations. The dose of montelukast may be adjusted.

Rationale for study duration: From the study team's experience with other interventional studies evaluating albuminuria and vascular endothelial function changes can be seen in 4-6 weeks. Changes in aPWV can be seen after 12 weeks. Changes in patients with CKD stage 3 may require longer periods of time for these endpoints and published data use a period of 3-6 months.^{42,44} Hence, we are proposing a 3-month intervention for this pilot study.

Data Collection

- Demographics, medical history and physical examination will be performed at screening or baseline visit.
- **Circulating measures:** Subjects will report fasted for standard blood chemistry analysis at baseline and 3 months. A urine pregnancy test will be performed if clinically indicated at the screening visit.
- **Outcome measures:**
 - 24-hour albuminuria will be measured at baseline and 3 months
 - EndoPat and aPWV will be measured at baseline and 3 months.
 - Urinary LTE₄, MCP-1, and CD163 will be measured at baseline and 3 months.
 - Plasma TNFR-1 and basic metabolic panel will be measured at baseline and 3 months.
- **Resting BP:** Arterial BP will be measured in triplicate while seated at rest using an automated oscillometric machine (Dinamap) at all in-person study visits.
- **Measures of adherence and safety:**
 - Pill counts will be assessed at the 3-month visit to document subject adherence.

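### Pregnancy is an exclusion, but the only pregnancy test is discretionary and confined to screening, and no negative result is required before study drug is dispensed

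*Combined protocol and SAP*

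**What the plan says.** All references are to the combined protocol and SAP, section IV (Research Methods), unless stated otherwise.

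- **Exclusion (Table 1):** "Pregnancy or planning to become pregnant or currently breastfeeding".
- **Population (Subjects):** "Men and women age 30-70 years of all races/ethnicities will be included". The plan expects some of the women to be premenopausal, because it schedules their vascular tests by cycle day (Outcome Measures, Secondary Outcome, Vascular endothelial function).
- **Testing (Data Collection, Circulating measures):** "A urine pregnancy test will be performed if clinically indicated at the screening visit". No other pregnancy test appears in the text available for review.
- **Screening (Rigorous Experimental Design):** "Subjects will undergo screening for inclusion/exclusion criteria during a 1-2 week period". The eligibility tests named there are urine albumin/creatinine and a basic metabolic panel. The list of baseline measurements has no pregnancy test.
- **History (Data Collection):** "Demographics, medical history and physical examination will be performed at screening or baseline visit".
- **Supply (Study Drug Dosing):** "Each bottle will contain 90 tablets of montelukast 10mg", taken once a day. The paragraph sets no condition on dispensing.
- **Hazard (safety section, item 8, Pregnancy):** use in pregnancy is to be reserved for clear need. Limb defects have been reported rarely without an established causal link, and no teratogenicity was seen in rats and rabbits at about 100 and 110 times the maximum adult dose.

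**The concern.** An exclusion protects participants only if someone checks it before exposure begins. Here the check rests on an undefined clinical judgement made at one visit, and no later step asks for a result before tablets are handed over.

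There is also an ordering problem. If history and examination are taken at baseline, as the plan allows, the information that would make a test indicated can arrive after the only visit at which a test is provided for.

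What is at stake is participant and fetal safety: an unrecognised early pregnancy at the start of treatment in an open-label pilot of an unproven use. By the protocol's own account there are no adequate controlled data in pregnancy. Nothing in the regression analysis of albuminuria or of the secondary outcomes depends on this.

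**Working it through.** The plan gives no figure on this point, so there is none to reproduce. The check is a comparison of provisions, with three small calculations.

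**1. What stands between a woman of childbearing potential and the first tablet?**

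| Step | Provision | Requires a negative test? |
|---|---|---|
| Screening | Test at clinical discretion; pregnancy is an exclusion | No, but a positive result excludes |
| Screening or baseline | History and examination | No |
| Baseline | Vascular tests, timed to cycle days 1-6 if premenopausal | No |
| Dispensing | One 90-tablet bottle | No |

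Required tests before dispensing: 0. Discretionary tests: 1.

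**2. How strong is the cycle-day rule?** The plan states that "EndoPat and aPWV will be measured at baseline and 3 months". Aim 2 compares vascular function before and after therapy, so the baseline measurement has to precede treatment to be usable. A premenopausal woman would normally need a recent period to be scheduled, and that catches most unrecognised pregnancies. However, the rule's stated purpose is to control for the cycle, it is not a condition for dispensing, and irregular bleeding can mislead it.

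**3. How old could a screening result be?** Screening lasts 1 to 2 weeks. A test on the first day of a two-week screening would be 2 × 7 = 14 days old when screening ends. The intervals from there to the baseline visit and to the first tablet are not given.

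**4. How much drug is handed over?** 90 tablets ÷ 1 per day = 90 days, the whole treatment period.

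**5. What would testing cost?** Let k be the number of enrolled women of childbearing potential. The plan does not give k, so take the full range 0 to 20. Two tests each gives 2 × k, from 2 × 0 = 0 to 2 × 20 = 40 strips. Women who are tested and then fail screening would add to this.

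**The case against.** The strongest reply is that the test provision already does the job. In a trial of men and women up to age 70 that excludes pregnancy, the natural meaning of a test on clinical indication is a test in women who could be pregnant. On that reading, omitting the test in such a woman would depart from the protocol. A positive result at screening already bars entry, and the cycle-day rule provides a second barrier at baseline. Consent pages were removed from the text available here and may contain pregnancy precautions. The hazard itself is modest on the protocol's own description.

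Most of this stands, and it is why the point is small. It does not close the gap completely. The intended meaning is not written down, the test remains tied to screening while history may come later, and no result is linked to dispensing.

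A reader might infer three stronger things, and the documents support none of them:

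- **That the protocol permits dosing a pregnant woman.** It does not. Doing so would breach Table 1 whenever it came to light. At most, leaving out the test might not count as a deviation.
- **That women will certainly start untested.** This depends on a narrow reading of an undefined phrase.
- **That the single bottle and the possibly remote contacts ("The follow-up schedule includes assessments at 3 months with monthly safety visits (either via phone, in person, or survey link") enlarge this gap.** Those features concern exposure after dispensing. A pre-dose test does nothing about conception during treatment, so they are not an argument for it.

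**Conclusion.** The point holds as a cheap, optional improvement in participant safety. The stated exclusion has no mandatory verification before a 90-day supply is given, and the one discretionary test may come before the history that would prompt it.

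The residual risk is very small. No number of affected pregnancies can be derived, because the plan gives neither the number of women of childbearing potential nor the interval from screening to first dose.

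The conclusion assumes that the available text is complete on testing, apart from the consent pages, and that no local procedure already requires a negative result. If such a procedure exists, the change only writes it down.

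**What to change.** In section IV, Data Collection, Circulating measures, put this in place of the present testing sentence:

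> All women of childbearing potential (premenopausal and not surgically sterile) will have a urine pregnancy test at screening, repeated on a spot urine sample at the baseline visit; study drug is dispensed only after a negative baseline result.

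This keeps a screening test, so that a pregnant woman is not taken through the 24-hour collection, fasting and vascular tests before being excluded. It adds the pre-dose check and defines who is tested. A spot sample is specified because the documents do not show that the pooled 24-hour specimen suits a pregnancy strip.

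**Cost:** one sentence, the strips counted above, and a short wait for the result before dispensing.

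**Limits:** a urine strip can miss a very recent conception, and conception during the 3 months of treatment would still not be detected.

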 - A neuropsychiatric assessment will be performed monthly to assess for any changes in mood, depression or anxiety symptoms via phone, in person, or survey link. We will utilize the Patient Health Questionnaire-9 (PHQ-9) and the General Anxiety Disorder-7 (GAD-7). These questionnaires will assess depression and anxiety symptoms, as well as any suicidal ideations and are routinely used in patients with CKD.^{45,46} We chose these questionnaires as they are validated in patients with CKD and can be completed in 10 minutes.^{45,46} Any participant that has a significant change in score from the

previous month or that reports suicidal ideations, will be referred immediately to [name], Co-I. [name] is a clinical psychologist. She will contact the patient and do a risk assessment to determine if the participant needs urgent mental health treatment. Participants that require urgent psychiatric care will be discontinued on study drug and removed from the study. We will also assess sleep including insomnia, sleepwalking etc. Finally, we will assess whether the participant is experiencing any memory problems, tremor or uncontrolled muscle movements. Participants that report these issues will be instructed to stop the study drug immediately. Participants will also be informed at study initiation to stop the drug and call immediately should they experience any change in mood, depression, aggression, agitation, sleep disturbances, or suicidal thoughts.

- Adverse event assessment will be performed monthly either via telephone, in person, or survey link. Additional telephone calls and PRN follow-up visits will occur at the discretion of the PIs.

Safety monitoring and expected adverse events: Reporting of Side Effects. Subjects will be instructed to report serious or worrisome side effects to the investigators and their primary care physician (who will have been informed of their patient's participation in and the nature of the study). A subject experiencing side effects during off hours will contact [name], who is available 24 hours a day. [name] will be on call during any period when [name] is not available. Thus, the physicians on the study team will work together to provide 24/7 medical coverage to subjects. Any unexpected adverse events will be reported immediately to the Colorado Institutional Review Board.

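### The PHQ-9/GAD-7 referral rule compares each score only with the previous month, and no score before the drug is scheduled; a baseline score and a comparison with it would be a cheap safety gain

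*Combined protocol and SAP*

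**What the plan says.** Under Measures of adherence and safety the protocol states: "A neuropsychiatric assessment will be performed monthly to assess for any changes in mood, depression or anxiety symptoms". The instruments are the PHQ-9 and GAD-7, with a stated completion time of 10 minutes. The referral rule that follows is "Any participant that has a significant change in score from the" and then "previous month or that reports suicidal ideations, will be referred immediately to" the study's clinical psychologist. No cut-off for a significant change is given.

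The timing of the first score has to be inferred from other parts of IV. Research Methods:

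- **Baseline.** The list introduced by "During the baseline phase the following will be measured" covers albuminuria, vascular function, chemistry, urine markers and plasma TNFR-1. It contains neither questionnaire.
- **Screening and Data Collection.** The other pre-drug items are urine albumin/creatinine, a metabolic panel, demographics, history, physical examination and, where indicated, a pregnancy test. Again there is no questionnaire.
- **Follow-up.** "The follow-up schedule includes assessments at 3 months with monthly safety visits". The monthly contacts are placed here, after the drug has started.

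The Baseline list is not exhaustive. Resting blood pressure is missing from it, although Data Collection requires it "at all in-person study visits". The absence of the questionnaires is therefore silence and does not prove that no baseline score is intended.

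**The concern.** Neuropsychiatric reaction is the one side effect that the safety section calls serious, and the section notes the boxed warning. It names monthly questionnaires as a way of detecting such reactions. The change that matters for safety is the change since starting the drug, and the score rule names no comparator for it.

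Two patterns can escape a rule that looks back only one month. One is steady worsening in steps that are each too small to trigger referral. The other is a large early rise that then persists, if there is no score before month 1 to set it against. With no control arm, a participant's own pre-drug score is the only score reference the trial could have for separating existing symptoms from new ones. It would not by itself attribute a change to montelukast.

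**Working it through.** The plan states no figure on this point, so there is none to reproduce. The check counts comparisons, tests the rule on simple score paths and sets out the risk context.

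**Inputs from the protocol:** 20 participants; 2 questionnaires; monthly assessment over 3 months; 10 minutes to complete; sleep disturbance, depression and agitation in up to 1 in 100 (safety section, item 1).

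**1. Comparisons with a pre-drug score.** Write M0 for a score before the first tablet and M1, M2, M3 for the monthly scores.

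| Reading | Comparisons made | On-treatment scores compared with M0 |
|---|---|---|
| A: scores start at month 1 | M2−M1, M3−M2 | 0 of 3 |
| B: monthly includes month 0 | M1−M0, M2−M1, M3−M2 | 1 of 3 |
| With the fix | B plus M2−M0, M3−M0 | 3 of 3 |

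With every questionnaire completed, there are 20 × 2 × 3 = 120 on-treatment scores. Those compared with a pre-drug score number 20 × 2 × 0 = 0 (A), 20 × 2 × 1 = 40 (B) and 20 × 2 × 3 = 120 (fix). These are counts of comparisons, not of patients harmed.

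**2. Score paths.** The plan gives no cut-off, so a referral threshold of T points is an assumption, varied from 3 to 6.

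- *Gradual rise of T−1 points a month.* Every monthly difference is T−1, below T, so the previous-month rule never fires under A or B. By month 3 the score is 3(T−1) above the start: 6, 9, 12 and 15 points for T = 3, 4, 5 and 6. A comparison with M0 sees 2(T−1) at month 2, which is at least T for each of these values, so it fires at months 2 and 3.
- *Jump of 2T by month 1, then flat.* Under A, M2−M1 and M3−M2 are both 0 and the rule never fires. Under B it fires once, at month 1. A comparison with M0 fires at all three months.

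**3. Risk context.** At 1 in 100 for the group of reactions, 20 × 0.01 = 0.2 cases are expected, and the chance of at least one is 1 − 0.99^20 = 0.182. At assumed lower rates of 0.5% and 0.1% that chance is 9.5% and 2.0%. If instead 1 in 100 applied to each of the three reactions without overlap, which is an assumption, 20 × 0.03 = 0.6 cases would be expected and the chance would be 1 − 0.97^20 = 0.456. These figures describe any case occurring, not a case being missed.

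**4. Cost.** 20 × 10 = 200 minutes, about 3.3 hours for the whole trial.

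**The case against.** The score rule is one layer of several. Suicidal ideation triggers referral on its own. Participants are told to stop the drug and call if their mood changes. Sleep, memory, tremor and movements are asked about, adverse events are reviewed monthly, and there is a further safety check two weeks after the last visit. The safety section provides for the psychologist to assess anyone who shows symptoms at once and for the drug to be stopped. That trigger depends on symptoms being present, so it needs no baseline score. Entry criteria also lower the risk: "History of major psychiatric disorder" is an exclusion, as is use of corticosteroids or long-acting beta-agonists.

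Reading B is also a natural one, because a previous-month rule cannot work at month 1 without a month-0 score. The gradual-rise example is a constructed worst case under an assumed cut-off, and adding a baseline comparison leaves significant worsening undefined.

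Most of this stands, and it limits the weight of the point. It does not close the gap. Stop-and-call relies on the participant noticing a change, which is harder when worsening is slow. What counts as having symptoms is not defined. Monthly contact may be by survey link, which may leave less room for clinical judgement. Reading B still leaves months 2 and 3 without a comparison to the pre-drug level.

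**Conclusion.** The concern holds. As written, the score rule compares with the previous month only, and no pre-drug PHQ-9 or GAD-7 is stated. Between 0 and 1 of the 3 on-treatment scores per questionnaire is formally compared with the pre-drug level, depending on the reading; it could be 3 of 3. The conclusion that months 2 and 3 lack this comparison does not depend on which reading is right or on any cut-off. The score-path examples do assume a cut-off.

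The point is modest. It is an improvement to a layered safety plan, not a finding that safety monitoring is absent. At the protocol's upper rate for the group of reactions, at most 0.2 cases are expected among 20 participants. The number that every other route would miss cannot be derived from the documents. No endpoint or efficacy analysis changes. The change is still worth making, because the risk carries a boxed warning, the trial is single-arm and the cost is small.

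**What to change.** Add the PHQ-9 and GAD-7 to the baseline measurements, to be completed before the first tablet. Amend the referral rule so that a significant worsening from baseline triggers referral, as well as one from the previous month. The same edit is the place to state what size of change counts as significant, since neither comparison is fully specified without it.

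The cost is about 10 minutes per participant at an existing visit, or 200 minutes in total. If a month-0 assessment is already intended, only the wording changes. The likely downside is a few more referrals to the psychologist.

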1. **Montelukast** is well tolerated and has been used in pediatric and adult patients for many years. The most common adverse reactions (incidence $\geq 5\%$ and greater than placebo) include upper respiratory infection, fever, headache, pharyngitis, cough, abdominal pain, diarrhea, otitis media, influenza, rhinorrhea, sinusitis and otitis. These side effects are minor and will be assessed on a monthly basis via phone, in person, or survey link. **A serious side effect** of montelukast is a neuropsychiatric adverse reaction. This reaction has been reported in patients with and without a history of psychiatric illness. This has been added as a Black Box Warning by the FDA. Reactions include agitation, aggressive behavior, anxiety, depression, restlessness, suicidal ideations or tendencies. Some patients also develop sleep disturbances (abnormal dreams, insomnia, sleep walking). Additionally disturbances in attention or memory impairment, tremor or involuntary movements may occur (up to 1 in 1,000 people). Sleep disturbances, depression and agitation may affect up to 1 in 100 people taking montelukast. Suicidal behavior and hallucinations occur very rarely (up to 1 in 10,000 people). We will assess for these serious adverse events monthly through the use of questionnaires regarding depression, anxiety and sleep via phone, in person, or survey link. We will also assess for any new tremors or involuntary movements. [name], Co-Investigator, is a clinical psychologist and researcher and will immediately do a risk assessment on any participant presenting with symptoms to determine if urgent psychiatric treatment is required and will arrange for treatment. Additionally, study drug will be stopped immediately. Most of these reactions resolve with stopping montelukast. We will exclude patients with a history of major depressive disorder, or that are on corticosteroids (inhaled or systemic) or long-acting beta-agonists as this may increase the risk of neuropsychiatric reactions.

2. **Fasting:** There is a small risk that blood sugars will be lower than normal in participants with diabetes while fasting. Participants will also be asked to check their blood sugars while fasting. If participants are unable to be fasting for 12 hours, they will be allowed to have a small snack prior to the study measurements. The fasting instructions for this study is similar to what we have prescribed in our other studies in participants with CKD with and without diabetes.

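### The plan commits to monthly assessment of the listed neuropsychiatric reactions, but its monthly check names no item for aggression, agitation, restlessness, attention problems or hallucinations

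*Combined protocol and SAP*

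**What the plan says.** Three places in Research Methods describe the same safety risk.

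**Risk description** (Safety monitoring and expected adverse events, item 1, Montelukast). The protocol calls the neuropsychiatric reaction serious and notes: "This has been added as a Black Box Warning by the FDA". It continues: "Reactions include agitation, aggressive behavior, anxiety, depression, restlessness, suicidal ideations or tendencies". Sleep disturbances follow, with abnormal dreams, insomnia and sleepwalking as examples. Upper rates are then given: 1 in 1,000 for problems of attention, memory or movement; 1 in 100 for a group that includes agitation; and for the rarest reactions, "Suicidal behavior and hallucinations occur very rarely (up to 1 in 10,000 people".

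The commitment comes next: "We will assess for these serious adverse events monthly through the use of questionnaires regarding depression, anxiety and sleep". One further sentence adds a check for new tremor or involuntary movements.

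**Monthly check** (Measures of adherence and safety). This is an assessment of change in mood, depression or anxiety using the PHQ-9 and GAD-7, which are described as covering depression, anxiety and suicidal ideation. Sleep questions are added, and then: "Finally, we will assess whether the participant is experiencing any memory problems, tremor or uncontrolled muscle movements". Contact may be by phone, in person or by survey link.

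**Instruction to participants** (same section). At study start they are told to stop the drug and call "should they experience any change in mood, depression, aggression, agitation, sleep disturbances, or suicidal thoughts".

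A general monthly adverse event assessment is also planned, by the same modes of contact, with no symptom content stated.

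**The concern.** The commitment refers back to the whole list of reactions, but the procedure described does not name all of them. This is the one risk that the protocol singles out as serious. The investigators evidently did not want to rely on general enquiry for it, since they added specific questions on sleep, memory, tremor and movement. The symptoms left without a named question come from the same list.

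What is at stake is how a low count can be read. Reactions that are asked about each month and reactions that are left to the participant to raise are ascertained differently. A low or zero count for the second group is weaker evidence of absence, and counts may be too low. The pilot is meant to inform a larger trial of whether montelukast may be a safe option, so the difference should not be built in by accident.

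**Working it through.** The protocol gives no figure of its own to reproduce here. The check is a comparison of lists, followed by a calculation for scale.

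**Step 1: compare the lists.** Splitting the risk description into single reactions, and counting suicidality once, gives 14. Abnormal dreams are credited to the general sleep questions.

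| Reaction in the risk description | Named in monthly check | Named in instruction at study start |
|---|---|---|
| Depression | yes | yes |
| Suicidality | yes | yes |
| Abnormal dreams, insomnia, sleepwalking (3) | yes | yes, as sleep disturbance |
| Anxiety | yes | no |
| Memory impairment | yes | no |
| Tremor | yes | no |
| Involuntary movements | yes | no |
| Agitation | **no** | yes |
| Aggressive behavior | **no** | yes |
| Restlessness | **no** | **no** |
| Attention disturbance | **no** | **no** |
| Hallucinations | **no** | **no** |

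Nine of 14 have a stated monthly check and 14 − 9 = 5 do not. Two of those five are in the instruction at study start, which leaves 5 − 2 = 3 in neither list.

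**Step 2: how many cases could arise.** Inputs: n = 20 participants (Hypotheses and Specific Aims; Subjects) and the upper rates p in the risk description. Expected cases = n × p. Chance of at least one case = 1 − (1 − p)^n.

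- Agitation, p = 0.01: expected 20 × 0.01 = 0.2; chance 1 − 0.99^20 = 18.2%.
- Attention disturbance, p = 0.001: expected 0.02; chance 1 − 0.999^20 = 2.0%.
- Hallucinations, p = 0.0001: expected 0.002; chance 1 − 0.9999^20 = 0.2%.
- Aggression and restlessness: no rate is given, so none is computed.

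With 18 participants (20 less the 10% attrition reported for the earlier vitamin D trial) the chances are 16.5%, 1.8% and 0.2%.

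**Step 3: what these figures mean.** They are chances that a case occurs. The chance that a case is missed also depends on how often the other routes would pick it up, which the documents do not give. For agitation it lies between 0% (every case is reported anyway) and 18.2% (none is).

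**The case against.** The three lists serve different purposes (describing risk, checking monthly, instructing participants), so unequal wording is not in itself a contradiction. Other routes also exist: the instruction at study start, a monthly adverse event assessment, a request to report troublesome side effects, round-the-clock physician cover and a safety check two weeks after the last visit. The sentence after the commitment adds tremor and movements, so the questionnaires are not presented as the whole assessment. The stated purpose of the pilot is to supply parameters for sizing a larger trial, and with at most 0.2 expected cases of agitation no rate is well estimated however it is asked.

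Much of this stands, and it rules out several stronger readings that a reader might infer:

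- *These reactions would go undetected, or a zero would simply mean that nobody asked.* Not supported: adverse events are assessed monthly, and aggression and agitation are named to participants.
- *The psychologist's risk assessment would not be triggered.* Contradicted: the Montelukast item applies it to anyone who presents with symptoms, not only to those with changed questionnaire scores.
- *No questionnaire item touches these symptoms.* Not shown: the PHQ-9 and GAD-7 items, the sleep questions and the adverse event form are not reproduced. Only the absence of a named item is established.
- *All five are boxed-warning reactions.* Agitation, aggression and restlessness are in the list directly after that statement. Attention problems and hallucinations come later, as further reactions.
- *18.2% is the chance of missing a case.* It is the chance that a case of agitation occurs.

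What the objection does not remove is the mismatch itself. The instruction at study start is given once and depends on participants recognising and reporting the symptom. The monthly adverse event enquiry has no stated symptom content, and by survey link there may be no interviewer to probe. Even if a questionnaire item touches agitation or attention, the stated questionnaire triggers for referral are a significant score change or suicidal ideation, so an isolated answer need not be followed up or recorded as an event.

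**Conclusion.** The point holds as a gap in active, structured questioning. The protocol commits to monthly assessment of the reactions it lists, and 5 of 14 have no named monthly item. It is most secure for aggression and hallucinations, and less so for agitation, restlessness and attention problems, which the questionnaires may touch. The gap is widest for restlessness, attention problems and hallucinations, which are named in neither the monthly check nor the instruction to participants.

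The practical size is small. Counts for these symptoms may be too low, but few cases are expected in 20 participants. The figures assume that the protocol's upper rates apply to this population over three months and that participants are independent. The case for acting rests on the seriousness that the protocol gives this risk and on the low cost of the change, not on the expected number of events.

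**What to change.** Use one symptom list in all three places: the risk description, the monthly check and the instruction to participants. Check it against the actual PHQ-9, GAD-7 and sleep items. For each listed symptom that no item covers, add a direct yes/no question to the existing monthly form. Aggression and hallucinations are the clearest candidates; agitation, restlessness and attention problems should be added if the questionnaires prove not to ask about them. Record each answer at symptom level, so that a negative reply can be told apart from a question not asked.

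The cost is a wording amendment, up to five short questions, about a minute more per contact and a few more reports to follow up. What is done with study drug for each symptom is for the investigators to reconcile between Measures of adherence and safety and the Montelukast safety item; no clinical rule is proposed here.
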